6.3.3 Type 1 Diabetes Mellitus or \geq Grade 3 Hyperglycemia

- Type 1 diabetes mellitus (T1DM), if new onset, including diabetic ketoacidosis (DKA)
- Grade 3 or higher hyperglycemia, if associated with ketosis (ketonuria) or metabolic acidosis (DKA)
- For **T1DM** or **Grade 3-4** Hyperglycemia
 - Insulin replacement therapy is recommended for Type I diabetes mellitus and for Grade 3-4 hyperglycemia associated with metabolic acidosis or ketonuria.
- Evaluate patients with serum glucose and a metabolic panel, urine ketones, glycosylated hemoglobin, and C-peptide.

6.3.4 Hypophysitis

- For Grade 2 events, treat with corticosteroids. When symptoms improve to Grade 1 or less, steroid taper should be started and continued over no less than 4 weeks. Replacement of appropriate hormones may be required as the steroid dose is tapered.
- For Grade 3-4 events, treat with an initial dose of IV corticosteroids followed by oral corticosteroids. When symptoms improve to Grade 1 or less, steroid taper should be started and continued over no less than 4 weeks. Replacement of appropriate hormones may be required as the steroid dose is tapered.

6.3.5 Hyperthyroidism or Hypothyroidism

Thyroid disorders can occur at any time during treatment: Monitor patients for changes in thyroid function (at the start of treatment, periodically during treatment, and as indicated based on clinical evaluation) and for clinical signs and symptoms of thyroid disorders.

- **Grade 2** hyperthyroidism events (and **Grade 2-4** hypothyroidism):
- In hyperthyroidism, non-selective beta-blockers (e.g. propranolol) are suggested as initial therapy.
- In hypothyroidism, thyroid hormone replacement therapy, with levothyroxine or liothyronine, is indicated per standard of care.
- **Grade 3-4** hyperthyroidism:
- Treat with an initial dose of IV corticosteroid followed by oral corticosteroids. When symptoms improve to Grade 1 or less, steroid taper should be started and continued over

no less than 4 weeks. Replacement of appropriate hormones may be required as the steroid dose is tapered.

6.3.6 Hematologic

- For **Grade 2** events, treat with oral corticosteroids, if indicated.
- For **Grade 3-4** events, treat with systemic or oral corticosteroids, as appropriate.

6.3.7 Hepatic

- For **Grade 2** events, monitor liver function tests more frequently until returned to baseline values (consider weekly).
 - Treat with IV or oral corticosteroids
- For **Grade 3-4** events, treat with intravenous glucocorticosteroids for 24 to 48 hours.

When symptoms improve to Grade 1 or less, a steroid taper should be started and continued over no less than 4 weeks.

In addition, the event must be reported as a Drug Induced Liver Injury (DILI) ECI, if the patient meets the laboratory criteria for potential DILI defined as:

- An elevated alanine transaminase (ALT) or aspartate transaminase (AST) lab value that is greater than or equal to three times (3X) the upper limit of normal (ULN) and
- An elevated total bilirubin lab value that is greater than or equal to two times (2X) ULN and at the same time, an alkaline phosphatase (ALP) lab value that is less than 2X ULN,
- As a result of within-protocol-specific testing or unscheduled testing.

6.3.8 Neurologic

- For **Grade 2** events, consider treatment with corticosteroids, as appropriate.
- For **Grade 3-4** events, treat with systemic corticosteroids. If condition worsens, consider IVIG or other immunosuppressive therapies, as per local guidelines.

When symptoms improve to Grade 1 or less, a steroid taper should be started and continued over no less than 4 weeks.

6.3.9 Ocular

- For **Grade 2** events, treat with topical steroids, such as 1% prednisolone acetate suspension and iridocyclitics.
- For **Grade 3-4** events, treat with systemic corticosteroids. When symptoms improve to Grade 1 or less, a steroid taper should be started and continued over no less than 4 weeks.

6.3.10 Renal Failure or Nephritis

- For **Grade 2** events, treat with corticosteroids.

- For **Grade 3-4** events, treat with systemic corticosteroids.

When symptoms improve to Grade 1 or less, a steroid taper should be started and continued over no less than 4 weeks.

6.3.11 Skin***

- For **Grade 2** events, symptomatic treatment with topical glucocorticosteroids or urea-containing creams, in combination with oral anti-pruritics.
- For **Grade 3-4** events, treat with systemic corticosteroids. When symptoms improve to Grade 1 or less, a steroid taper should be started and continued over no less than 4 weeks.

***Both pembrolizumab and cetuximab can cause a significant incidence of grade 2 / 3 rash. For a \geq grade 3 maculopapular rash (grading predominantly determined by degree of BSA involvement), which is strongly felt to be related to cetuximab and which is tolerable to the patient, additional supportive measures may be instituted with weekly clinical follow-up, without the initial addition of systemic corticosteroids. Pembrolizumab must be held, however, as noted above. This course of action should be discussed with the PI.

NOTE: Refer to the ECI Guidance Document (Section 3.9.1: Immediate Evaluation for Potential Skin ECIs) for detailed evaluation and reporting requirements.

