6 TREATMENT PLAN

6.1 Dosing and Administration

The treatment regimen to be used in this trial is outlined below:

Cetuximab 400 mg/m² loading dose on day 1 cycle 1, followed by 250 mg/m² intravenously weekly. Pembrolizumab 200 mg fixed dose intravenously every 3 weeks.

Reported adverse events (AEs) and potential risks are described in **Section 1.5**. Appropriate dose modifications are described in **Section 6.1**

A cycle is defined as 3 weeks of treatment, with cetuximab administered weekly and pembrolizumab administered every 3 weeks, on day 1 of each cycle. Absent relevant limiting toxicities, pembrolizumab may be administered even if cetuximab is to be held on day 1 for cetuximab related AEs. Likewise, in the instance of pembrolizumab related AEs which require dose holding or discontinuation, cetuximab administration should continue as appropriate. Cetuximab will be administered prior to pembrolizumab on day 1, due to concern for infusion reactions. Pembrolizumab may be administered on Day 2 of any cycle in the event of a Cetuximab related infusion reaction; or any other adverse event at the discretion of the PI.

If cetuximab is held for greater than 2 weeks for reasons other than cetuximab related adverse events, the 400 mg/m² loading dose may be readministered upon resumption, at the discretion of the investigator.

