6.1.1 Pembrolizumab

Dose Selection

Pembrolizumab 200 mg will be administered as a 30 minute IV infusion every 3 weeks. Sites should make every effort to target infusion timing to be as close to 30 minutes as possible. However, given the variability of infusion pumps from site to site, a window of 5 minutes and +10 minutes is permitted (i.e., infusion time is 30 minutes: -5 min/+10 min).

The package insert contains specific instructions for the preparation of the pembrolizumab infusion fluid and administration of infusion solution.

Timing of Dose Administration

Trial treatment will be administered on Day 1 of each cycle after all procedures/assessments have been completed (as detailed in **Table 4** Schedule of Procedures and Observations). Of note, the results of laboratory tests which are send-out tests (including TFTs) are not necessary prior to treatment. Pembrolizumab is to be administered after cetuximab infusion is complete. Trial treatment may be administered up to 3 days before or after the scheduled Day 1 of each cycle due to administrative reasons.

All trial treatments will be administered on an outpatient basis.

Pembrolizumab Dose Modification and Treatment Delay Guidelines

Adverse events (both non-serious and serious) associated with pembrolizumab exposure may represent an immunologic etiology. These adverse events may occur shortly after the first dose or several months after the last dose of treatment. Pembrolizumab must be withheld for drug-related toxicities and severe or life-threatening AEs as per **Table 1**. See **Section 6.3** and Events of Clinical Interest Guidance Document for supportive care guidelines, including use of corticosteroids

The following dose modification rules will be used with respect to potential toxicity. Toxicity will be assessed according to the NCI Common Terminology Criteria for Adverse Events Version 4.0 (CTCAE v4.0).

Table 1 Dose Modification Guidelines for Drug-Related Adverse Events: Pembrolizumab

Toxicity	Hold Treatment For Grade	Timing for Restarting Treatment	Discontinue Subject
Diarrhea/Colitis	2 ¹	Toxicity resolves to Grade \leq 1 ¹	Resume once improved to Grade \leq 1
	3	Toxicity resolves to Grade \leq 1	Toxicity does not resolve within 12 weeks of last dose or inability to reduce corticosteroid to 10 mg or less of prednisone or equivalent per day within 12 weeks
	4	Permanently discontinue	Permanently discontinue

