AST, ALT, or Increased Bilirubin	2	Toxicity resolves to Grade \leq 1	Toxicity does not resolve within 12 weeks of last dose
	3-4	Permanently discontinue (see exception below) ²	Permanently discontinue
Type 1 diabetes mellitus (if new onset) or Hyperglycemia	T1DM or 3-4	Hold pembrolizumab for new onset Type 1 diabetes mellitus or Grade 3-4 hyperglycemia associated with evidence of beta cell failure	Resume pembrolizumab when patients are clinically and metabolically stable
Hypophysitis	2-3	Toxicity resolves to Grade \leq 1	Toxicity does not resolve within 12 weeks of last dose or inability to reduce corticosteroid to 10 mg or less of prednisone or equivalent per day within 12 weeks
	4	Permanently discontinue	Permanently discontinue
Hyperthyroidism	3	Toxicity resolves to Grade \leq 1	Toxicity does not resolve within 12 weeks of last dose or inability to reduce corticosteroid to 10 mg or less of prednisone or equivalent per day within 12 weeks.
	4	Permanently discontinue	Permanently discontinue
Infusion Reaction	3-4	Permanently discontinue	Permanently discontinue
Pneumonitis	2	Toxicity resolves to Grade \leq 1	Toxicity does not resolve within 12 weeks of last dose or inability to reduce

Toxicity	Hold Treatment For Grade	Timing for Restarting Treatment	Discontinue Subject
			corticosteroid to 10 mg or less of prednisone or equivalent per day within 12 weeks
	3-4	Permanently discontinue	Permanently discontinue
Renal Failure or Nephritis	2	Toxicity resolves to Grade \leq 1	Toxicity does not resolve within 12 weeks of last dose or inability to reduce corticosteroid to 10 mg or less of prednisone or equivalent per day within 12 weeks
	3-4	Permanently discontinue	
Rash³	3 or Severe ^{4,5}	Toxicity improves to Grade \leq 2	Toxicity does not improve within 12 weeks of last dose or inability to reduce corticosteroid to 10 mg or less of prednisone or equivalent within 12 weeks
All Other Drug-Related Toxicity,³	3 or Severe ⁴	Toxicity resolves to Grade \leq 1	Toxicity does not resolve within 12 weeks of last dose or inability to reduce corticosteroid to 10 mg or less of prednisone or equivalent per day within 12 weeks
	4	Permanently discontinue	Permanently discontinue

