
Note: Permanently discontinue for any severe³ or Grade 3 drug-related AE that recurs or any life-threatening event.
 
¹ For grade 2 diarrhea which is attributed to cetuximab and sub-optimally managed with anti-diarrheal agents, Pembrolizumab may be continued. Patients should be seen in clinical follow-up within 1 week with additional phone follow-up within 72 hours. If optimally managed with anti-diarrheal agents and it is not felt that the toxicity is clearly cetuximab related, Pembrolizumab should be held until toxicity resolves to Grade \leq 1.
 
² For patients with liver metastasis who begin treatment with Grade 2 AST or ALT, if AST or ALT increases by greater than or equal to 50% relative to baseline and lasts for at least 1 week then patients should be discontinued.
 
³ Patients with intolerable or persistent Grade 2 drug-related AE may hold study medication at physician discretion. Permanently discontinue study drug for persistent Grade 2 adverse reactions for which treatment with study drug has been held, that do not recover to Grade 0-1 within 12 weeks of the last dose.
 
⁴ For these purposes, a severe toxicity is a toxicity which does not otherwise meet the criteria for grade 3 or 4, but which the investigator deems as being substantial enough to merit the holding of therapy.
 
⁵ For an acneiform or maculopapular rash which is deemed to be clearly related to cetuximab, at the investigator's discretion, pembrolizumab may be administered even for grade 3 rash, as long as the rash is showing signs of improvement and cetuximab is held as per protocol.
			

Dosing interruptions are permitted in the case of medical / surgical events or logistical reasons not related to study therapy (e.g., elective surgery, unrelated medical events, patient vacation, and/or holidays). Participants should be placed back on study therapy within 3 weeks of the scheduled interruption, unless otherwise discussed with the Sponsor. The reason for interruption should be documented in the patient's study record.

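### For a tolerable, improving grade 3 maculopapular rash attributed to cetuximab, with cetuximab held, Table 1 footnote 5 permits pembrolizumab while Section 6.3.11 says to hold it and does not cite the exception

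*Combined protocol and SAP*

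**What the plan says.** Section 6.1.1 ties withholding to one table: "Pembrolizumab must be withheld for drug-related toxicities and severe or life-threatening AEs as per" Table 1. The rash row of that table holds pembrolizumab for grade 3 or severe rash, and its restart cell reads "Toxicity improves to Grade" 2 or lower. The hold cell carries footnote 5, which makes an exception. "For an acneiform or maculopapular rash which is deemed to be clearly related to cetuximab", the footnote leaves the decision to the investigator: "pembrolizumab may be administered even for grade 3 rash, as long as the rash is showing signs of improvement and cetuximab is held" according to the protocol.

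The starred note in Section 6.3.11 (supportive care, skin) deals with a rash at or above "grade 3 maculopapular rash (grading predominantly determined by degree of BSA involvement), which is strongly felt to be related to cetuximab" and tolerable to the patient. It allows added supportive measures with weekly clinical follow-up and without systemic steroids at the outset. It asks that this course be discussed with the PI. On the study drug it says "Pembrolizumab must be held, however, as noted above". It neither repeats nor cites footnote 5.

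Two other places bear on the question. Section 6.1 says that, if there are no relevant limiting toxicities, "pembrolizumab may be administered even if cetuximab is to be held on day 1 for cetuximab related AEs". The opening of Section 6.3 sends the reader to Section 6.1.1 for dose modification and says its treatment guidelines are meant for events judged related to pembrolizumab.

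**The concern.** Both texts address a maculopapular rash of grade 3 that the investigator attributes to cetuximab. One makes pembrolizumab permissible under stated conditions. The other is worded as an unconditional hold. A site that works from the supportive-care section sees no exception, and a site that works from the dose-modification table does.

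Rash is a foreseeable event here, since Section 6.3.11 itself says both drugs cause an appreciable incidence of grade 2 or 3 rash. The study runs at three sites (Section 4.2), pembrolizumab is given once every three weeks, and the adverse event profile is a primary objective (Section 3.1). What is at stake is a clear dosing instruction for patient safety, and consistency between sites in pembrolizumab exposure and in recorded dose holds.

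**Working it through.** The main check is a comparison of text. The plan states no figure to reproduce.

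**Step 1. The two rules side by side.**

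| Element | Table 1 footnote 5 (Section 6.1.1) | Starred note (Section 6.3.11) |
|---|---|---|
| Rash type | acneiform or maculopapular | maculopapular |
| Grade | 3 | 3 or higher |
| Attribution | clearly cetuximab | strongly felt to be cetuximab |
| Tolerability | no condition | tolerable to the patient |
| Course | improving | no condition |
| Cetuximab | held | no condition |
| Who decides | investigator's discretion | discuss with the PI |
| Pembrolizumab | may be given | must be held |

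**Step 2. The overlap.** Both texts apply to a rash that is maculopapular, grade 3, attributed to cetuximab, tolerable and improving, with cetuximab held. For that rash the last row gives two different instructions.

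**Step 3. Outside the overlap.** A grade 3 rash that is not improving fails the footnote's condition, so the Table 1 hold applies and agrees with Section 6.3.11. An acneiform rash is not covered by the starred note. A rash that has come down to grade 2 or lower meets the Table 1 restart point and is no longer the grade that the note describes. The disagreement is confined to Step 2.

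**Step 4. Whether cross-references resolve it.** The bullets earlier in Section 6.3.11 concern topical and systemic steroids and say nothing about holding pembrolizumab. The back-reference in the hold sentence therefore most naturally points to the Table 1 rash row, and the Section 6.3 opening supports that by referring to Section 6.1.1. That row contains both the hold and the footnote. The note applies the hold to the very rash the footnote exempts, and it does not say whether the exemption survives. The statement that Section 6.3 is for pembrolizumab-related events does not help either, because the note is expressly about a rash attributed to cetuximab.

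**Step 5. Size.** The documents give no rate for the overlap. Section 1.5 gives up to 5% for grade III/IV dermatologic reactions on cetuximab, and Section 1.2 gives at most 5% for grade III rash. With 42 patients (Section 4.2), the ceiling is 0.05 × 42 = 2.1 patients with any severe reaction of this kind.

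The overlap is a subset of those events. To show a range, with rates that are my assumptions and not the plan's, expected number = p × 42 and chance of at least one = 1 − (1 − p)^42:
- p = 1%: 0.42 patients; 1 − 0.99^42 = 0.34
- p = 2%: 0.84 patients; 1 − 0.98^42 = 0.57

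**Step 6. Effect on the design.** The hypotheses, sample size and type I error in Section 12.1 do not use rash or dosing rules. Section 12.5 leaves grade 3 rash out of the DLT definition. Section 12.4.1 tabulates toxicity by maximum grade within a patient, so the rash itself is counted at that grade whichever instruction a site follows.

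**The case against.** The strongest reply is that there is no contradiction. Section 6.3 is about supportive care and defers to Section 6.1.1 for dosing, so the hold in Section 6.3.11 merely restates Table 1 with its footnotes. The two texts may also describe successive moments: the note speaks of initial management, and the footnote takes effect only once the rash improves. Both readings are reasonable. Neither is written down in Section 6.3.11, and a reader of that section alone would not find the exception.

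Two further points stand and limit the concern. The footnote is permissive, so a site that holds pembrolizumab complies with both texts. The request to consult the PI may also reduce differences between sites.

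A reader might go further and infer that sites will treat the same event in opposite ways. The documents show only that they could, each in compliance.

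A reader might also take 2.1 expected patients and an 88% chance of at least one (1 − 0.95^42 = 0.88) as the expected frequency of the conflict. That is not supported. The 5% is a ceiling for all severe cetuximab skin reactions, and Section 1.2 describes the rash as often acneiform, which the starred note does not cover. The conflict also requires the rash to be improving yet still grade 3 when a three-weekly dose is due. In the other direction, 5% comes from cetuximab alone and does not bound the rate on the combination.

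Nor do the documents support calling this the most predictable overlapping toxicity: Section 1.5 lists diarrhea as well as rash for both drugs.

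**Conclusion.** The inconsistency is real but narrow. For the rash defined in Step 2, one passage permits a pembrolizumab dose and the other forbids it, and the text does not say which governs. This rests on reading Section 6.3.11 as written, without importing an exception it does not cite.

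The likely consequence is a difference between sites in one or a few pembrolizumab doses, in a small number of patients that the documents do not allow to be estimated. The only documented anchor is the ceiling of about 2 of 42 for the wider event on cetuximab alone. The statistical design is unaffected. The point merits correction because it concerns a dosing instruction for a foreseeable toxicity and is easy to settle. No view is taken on which instruction is right.

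**What to change.** Reconcile Table 1 footnote 5 with the starred note in Section 6.3.11 so that a single instruction on pembrolizumab applies to this event, and have each passage cite the other. The reconciled text should also say whether the decision rests with the investigator alone or follows discussion with the PI, since the two passages differ on that. The choice of instruction belongs to the clinical team.

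The cost is about one sentence and two cross-references in the next amendment. Sample size, analysis and data collection do not change.

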6.3.12 Other ECIs

The following AEs, regardless of grade, are considered ECIs and should be reported to the Sponsor (see Section 10.4.1)

- Myocarditis
- Pericarditis
- Pancreatitis
- Any additional Grade 3 or higher event which the investigator considers to be immune-related.
 - For **Grade 2** events, or **Grade 1** events that do not improve with symptomatic treatment: Systemic corticosteroids may be indicated.
 - For **Grade 3-4** events, treat with systemic corticosteroids. When symptoms improve to Grade 1 or less, a steroid taper should be started and continued over no less than 4 weeks.

6.3.13 Infusion Reactions

Signs and symptoms usually develop during or shortly after drug infusion and generally resolve completely within 24 hours of completion of infusion. **Table 3** shows treatment guidelines for participants who experience an infusion reaction associated with administration of pembrolizumab.

Table 3 Infusion Reaction Treatment Guidelines

NCI CTCAE Grade	Treatment	Premedication at subsequent dosing

Grade 1 Mild reaction; infusion interruption not indicated; intervention not indicated
	
Increase monitoring of vital signs as medically indicated until the subject is deemed medically stable in the opinion of the investigator.
	
None

Grade 2 Requires infusion interruption but responds promptly to symptomatic treatment (e.g., antihistamines, NSAIDS, narcotics, IV fluids); prophylactic medications indicated for <=24 hr.
	
Stop Infusion. Additional appropriate medical therapy may include but is not limited to:
 
 • IV fluids • Antihistamines • NSAIDS • Acetaminophen • Narcotics 
Increase monitoring of vital signs as medically indicated until the subject is deemed medically stable in the opinion of the investigator.
 
If symptoms resolve within one hour of stopping drug infusion, the infusion may be restarted at 50% of the original infusion rate (e.g., from 100 mL/hr to 50 mL/hr). Otherwise dosing will be held until symptoms resolve and the subject should be premedicated for the next scheduled dose.
 
Subjects who develop Grade 2 toxicity despite adequate premedication should be permanently discontinued from further trial treatment administration.
	
Subject may be premedicated 1.5 hr (\pm 30 minutes) prior to infusion of pembrolizumab (MK-3475) with:
 
 • Diphenhydramine 50 mg po (or equivalent dose of antihistamine). • Acetaminophen 500-1000 mg po (or equivalent dose of antipyretic).

Grades 3 or 4
 
Grade 3: Prolonged (i.e., not rapidly responsive to symptomatic medication and/or brief interruption of infusion); recurrence of symptoms following initial improvement; hospitalization indicated for other clinical sequelae (e.g., renal impairment, pulmonary infiltrates).
 
Grade 4: Life-threatening; pressor or ventilatory support indicated
	
Stop Infusion. Additional appropriate medical therapy may include but is not limited to:
 
 • IV fluids • Antihistamines • NSAIDS • Acetaminophen • Narcotics • Oxygen • Pressors • Corticosteroids • Epinephrine 
Increase monitoring of vital signs as medically indicated until the subject is deemed medically stable in the opinion of the investigator.
 
Hospitalization may be indicated.
 
Subject is permanently discontinued from further trial treatment administration
	
No subsequent dosing

Note: Appropriate resuscitation equipment should be available in the room and a physician readily available during the period of drug administration.

